4.4. Main outcomes and measures

4.4.1. Outcomes

The primary outcome will be measured only among patients who have not had a weight recorded in the EHR during the 6 months (180 days) prior to the ADHD medication refill request. We will determine whether the prescribing clinician attempted to ensure that the child had a weight checked or recorded, counting the outcome as present if (a) the patient was referred for an in-person visit for a weight check (including a well child visit or a nurse visit for a weight check), or (b) had a parent-reported weight recorded in the EHR. This outcome will be assessed via analysis of EHR data and chart review. Referral for a visit or weight check (part a above) will include any of the following:

- (a) the EHR record or chart review indicates that an appropriate in-person appointment was booked with pediatrics, family medicine, or psychiatry after the pharmacist or PCP handled the message;
- (b) a chart note indicates that the pharmacist or physician handling the RAR instructed the parent to schedule a follow-up appointment for a weight check;
- (c) a note in the EHR indicates that a medical assistant or other staff member had attempted to book a follow-up appointment for a weight check

Secondary outcomes will be the:

- a. Whether the child had a weight recorded within 30 days after the RAR, regardless of the reason for the weight being measured (this measure would count weights recorded at urgent visits)
- b. Hours from the secure message request to the prescription order being placed, among patients who had a prescription ordered
- c. Days from the secure message request to the prescription being filled (sold), among patients who had a prescription ordered
- d. Parent satisfaction with care, as measured by standardized survey items

Exploratory outcomes will be:

- a. Whether the provider initially handling the request was able to fully resolve it without referring it to another provider (first-touch resolution)
- b. Whether the patient had a refill prescribed (% of patients with refills prescribed)

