We will also ask parents to indicate the mode by which they would prefer to make future ADHD medication refill requests, e.g. secure message or a telephone, video, or in-person appointment.

4.6. Statistical analysis plan.

The primary analysis will treat each patient as part of the group to which their facility was assigned (intention-to-treat). However, some patients in the Pharmacist Care group might have unintentional crossover and be handled by physicians instead of pharmacists. For this reason, we will conduct a secondary analysis in which patients are grouped based on the initial management approach they actually received (pharmacist or physician, based on which type of clinician first contacted the patient), similar to a per-protocol analysis. An RAR first accessed by a pharmacist and later accessed by physician will be counted in the pharmacist group.

The primary outcome is binary, i.e., whether or not a patient who had not had a weight check in the 6 months before the refill request is referred for an appropriate follow-up visit. This will be compared between study groups using mixed effects logistic regression providing point and interval estimates of outcome odds ratios associated with study group. This analysis technique accounts for the within-facility and within-patient correlation to obtain valid estimates of treatment effects and associated standard errors. The pre-specified set of covariates for inclusion in regression models include: study group and covariates used in the randomization procedure (i.e. patient socioeconomic status (using the Neighborhood Deprivation Index), patient age, sex, race and ethnicity, and comorbidity score). Study group and other covariates will be treated as fixed effects and facility will be handled as a random effect.

In addition, exploratory/sensitivity analyses will examine the impact of including additional covariates in our estimation of treatment effect, with focus on variables with chance imbalance in distributions by treatment group, as determined in preliminary analyses. Analyses resulting in

an appreciable change in the estimate of treatment differences or increased precision of the treatment effect will be noted.

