For the secondary outcomes, we will compare the days from the secure message request to prescription order or medication fill between the Pharmacist Care and PCP Care groups using linear mixed regression models, providing point and interval estimates of between-group differences in mean outcomes. If the numbers of days have a skewed distribution, log transformation will be used. Analyses of other continuous secondary outcomes will be similar. The approach to inclusion of covariates and sensitivity/exploratory analyses is as described for Aim 1.

For patient satisfaction, care experience scores will be compared between the study groups using linear mixed effects regression with log transformation if needed for skewed data, with analyses paralleling that described for the secondary outcomes. For analyses, categorical responses will be combined into a binary variable (Excellent or Very Good vs. Good, Fair, or Poor).

For all aims, secondary analyses will assess variation in the estimates of treatment effect by age, sex, socioeconomic status (using the Neighborhood Deprivation Index), and race and ethnicity, via stratification by level of the potential effect modifier. These stratified analyses will inform the fitting of mixed effects regression models with appropriate cross-product terms between the potential effect modifier and study group indicator variable, allowing for a more formal assessment of heterogeneity in treatment effect.

A facility may drop out before completion of the study if they were assigned to PCP Care but add local pharmacist management, thus diverging from their assigned group. ADHD medication refill requests to such a facility will be censored as of the dropout date (the date that local pharmacist management began).

Tests of significance will be two-tailed with an alpha of .05. No Bonferroni or other formal correction for multiple comparisons will be used, but results will be interpreted with the multiple testing issue in mind.

4.8. Sample size and power. To estimate the available sample, we extrapolated from data analyzed during the pilot period in April 2024.

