Based on initial data in the pilot period, we estimate that the message pool handlers will send the regional pharmacy team 7 secure messages for straightforward ADHD medication refill requests per weekday, i.e., 35 eligible messages per week. We estimate based on expert opinion that 30% of these patients don't have a weight check in the previous 6 months. Assuming a 9-week evaluation period, the estimated sample size is 315 patients, or an average of 5 patients in each of the 63 clusters.

Given the group-randomization study design, calculation of sample sizes and minimum detectable treatment effects must account for the expected intraclass correlation (ICC) of observations within facilities. The ICCs in outcomes of interest are expected to be small, and therefore we present minimum detectable effects for an expected ICC of .03.

For Aim 1, the primary outcome is the % of patients without a weight check in the past 6 months who received referral for an appropriate follow-up visit. The following estimates assume that 30% of the 315 patients with secure messages will have not had a weight check in the past 6

months, for a sample size of 95 (63 clusters with 1.5 patients each). We also assume a desired power of 80%, a two-tailed alpha of 0.05 and an ICC of .03. If 50% of patients in the PCP Care group will receive an appropriate referral, the least detectable difference will 77%. If 80% of the patients in the PCP Care group receive an appropriate referral, the least detectable difference will be 98%. Thus, this sample size yields good power to identify only large differences between the two arms in the primary outcome.

For Aim 2, the outcome is days from the secure message to the prescription order. The following estimates assume a sample size of 315 (63 clusters with 5 patients each), a desired power of 80%, a two-tailed alpha of 0.05 and an ICC of .03. The least detectable effect size for a comparison of means will be 0.334. In other words, this study will have good power to find a statistically significant difference between the Pharmacist Care and PCP Care groups for a small to medium effect size.

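### The prespecified main model for time to order leaves out when the request arrived, a pre-handling variable already on file; this gives up some precision on a secondary outcome, by an amount the documents cannot fix.

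*Combined protocol and SAP*

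**What the plan says.** Section 4.4.1 defines secondary outcome b as "Hours from the secure message request to the prescription order being placed, among patients who had a prescription ordered". Sections 4.6 and 4.8 describe the same outcome in days (4.8: "For Aim 2, the outcome is days from the secure message to the prescription order"). No section defines the clock in business hours.

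Section 4.6 analyses the timing outcomes with "linear mixed regression models, providing point and interval estimates of between-group differences in mean outcomes", using a log transformation if the data are skewed. For covariates it adds: "The approach to inclusion of covariates and sensitivity/exploratory analyses is as described for Aim 1". The Aim 1 approach has two parts:

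- **Main model:** study group plus "patient socioeconomic status (using the Neighborhood Deprivation Index), patient age, sex, race and ethnicity, and comorbidity score", with facility as a random effect.
- **Further models:** "exploratory/sensitivity analyses will examine the impact of including additional covariates in our estimation of treatment effect, with focus on variables with chance imbalance". Any that change the estimate appreciably or improve its precision are to be noted.

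The covariate list in section 4.4.2 adds language spoken and is otherwise similar. Day of week, holiday and hour of arrival appear nowhere as a covariate, a stratifier, an effect modifier or a balancing variable for the randomization.

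**The concern.** The Aim 1 covariates describe the patient. Time to order also depends on when someone is available to act on the request. If a request sent on a Friday evening waits until Monday in either arm, calendar timing adds variation to the outcome that has nothing to do with who handles it. That variation stays in the residual and widens the interval for the Aim 2 comparison.

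The variable that could remove it is already held, because the request timestamp is the start point for computing the outcome. It is fixed before a pharmacist or physician touches that request, so adjusting for it does not absorb the effect of how the request is handled. At stake is precision on a secondary outcome that carries one of the trial's three aims.

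**Working it through.** **Inputs from the plan (section 4.8 and Appendix A).** N = 315 requests, 63 facilities, m = 5 per facility, ICC = 0.03, power 80%, two-sided alpha 0.05, least detectable effect 0.334 SD.

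**Step 1: reproduce the plan's figure.**
- Design effect = 1 + (m − 1) × ICC = 1 + 4 × 0.03 = 1.12.
- Detectable effect = (1.960 + 0.842) × √(4 × 1.12 / 315) = 0.334.

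This matches. ICCs of 0.01 and 0.05 give 0.322 and 0.346, as in Appendix A. The figure uses no covariate adjustment.

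**Step 2: assumed inputs.** None of these is in the documents.
- Share p of requests arriving on non-working days: 1/7 to 2/7 (14-29%), roughly an even spread over the week.
- Extra wait d for those requests: 24 to 48 h.
- Residual SD s, after removing arrival time: 36 h.

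**Step 3: share of within-facility variance explained.** R² = p(1 − p)d² / [p(1 − p)d² + s²], with s² = 1,296.
- Low end (p = 1/7, d = 24): 0.1224 × 576 = 70.5, so R² = 70.5 / 1,366.5 = 0.05.
- High end (p = 2/7, d = 48): 0.2041 × 2,304 = 470.2, so R² = 470.2 / 1,766.2 = 0.27.

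**Step 4: detectable effect after adjustment.** A request-level covariate mainly reduces the within-facility variance, so the between-facility part is held fixed:

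Detectable effect = 2.802 × √(4 × [m × ICC + (1 − ICC)(1 − R²)] / N)

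| Case | R² | Bracketed term | Detectable effect (SD) | Equivalent N gain (1.12 / bracketed term − 1) |
|---|---|---|---|---|
| No adjustment | 0 | 1.120 | 0.334 | 0% |
| Low end | 0.05 | 1.070 | 0.327 | 5% |
| High end | 0.27 | 0.862 | 0.293 | 30% |

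Multiplying 0.334 by √(1 − R²) would give 0.325-0.286. That also shrinks the between-facility variance, so it overstates the gain.

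**Step 5: simulation check.** 4,000 trials per setting used 63 facilities of 5, ICC 0.03, a true effect of 0.334 SD and known variance components. Unadjusted and adjusted power were 79.5% and 82.4% at R² = 0.10, and 79.0% and 90.1% at R² = 0.30. The formula gives 83% and 90% for the adjusted model.

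**Step 6: sensitivity on the log scale.** Section 4.6 would log-transform skewed times. With 15-50% of requests off-hours, a 1.5- to 4-fold delay and a residual SD of 0.8-1.2 on log hours (all assumed), R² runs from 0.01 to 0.43. The detectable effect then runs from 0.332 to 0.265, so the gain can be close to nothing.

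**Step 7: planned volume.** The 315 rests on 9 weeks at 35 per week, while section 4.1 gives a formal period of 7 weeks. Then 7 × 35 = 245 requests, about 3.9 per facility. The unadjusted detectable effect is 0.373, before restriction to patients with an order. The Step 3 inputs bring it to 0.364-0.326.

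**The case against.** The sentence that imports the Aim 1 covariates also imports its exploratory models, and these are aimed at chance imbalance. A reader might infer that the plan adjusts only for patient characteristics and that any imbalance in weekend requests passes unexamined into the arm difference. The documents do not support that reading. An analyst could add arrival time in an exploratory model and report any precision gained. Facilities are also randomized, so chance imbalance is not bias, and the interval from the main model already allows for it.

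A reader might also infer that arrival time is the main driver of hours to order. Nothing in the documents shows this. The count in section 4.8, "7 secure messages for straightforward ADHD medication refill requests per weekday", is pilot flow of free-text messages forwarded to the pharmacy team. Section 4.1 explains that the study was then limited to structured refill authorization requests. The count does not describe when those requests arrive, or weekend and evening coverage in either arm.

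Both objections stand and limit the point. They do not remove it: the exploratory covariates are unnamed, are selected mainly for imbalance, and do not supply the main estimate. A precision covariate is best chosen because it is expected to predict the outcome, and named before the data are seen.

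It is also fair that nothing here quantifies a gain for fill time. That outcome is counted in days until sale and may depend on when the family collects the medicine.

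**Conclusion.** The point holds as a free improvement. The prespecified main model omits a plausible predictor of a clock-hours outcome, although the timestamp is already needed to compute that outcome. The consequence is some loss of efficiency on a secondary outcome. It is not bias, and the 0.334 in section 4.8 is correct as calculated and relies on no covariate gain.

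Under the stated assumptions the detectable effect would fall from 0.334 to about 0.327-0.293 SD, equivalent to 5-30% more requests. Those figures rest on assumed arrival shares, delays and residual SD, on a raw-hours scale, and on non-working days only; after-hours arrival was not separately sized. Other inputs give a negligible gain. If the outcome were recorded in whole days, an after-hours effect would be diluted more than a weekend effect, so the hours and days wording should be settled first.

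**What to change.** In section 4.6, add two prespecified fixed effects to the main order-time model: arrival on a weekend or holiday (yes/no) and arrival after hours (yes/no). Derive both from the existing request timestamp, and write the definition of after hours into the plan before analysis. Use one unit for order time across sections 4.4.1, 4.6 and 4.8. Including the two terms in the fill-time model is optional.

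The cost is two extra parameters with about 245 to 315 requests and no new data collection. If arrival time proves weakly prognostic, almost nothing is lost. If off-hours coverage differs by arm, the arm effect may vary with arrival time; the main-effect terms then still yield an average effect.

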4.4.2. Predictors and covariates

The primary predictor is study group, i.e. Pharmacist Care or PCP Care. Covariates are other variables that could potentially mediate, moderate, or confound the association between the primary predictor and the outcomes. In this study, covariates include patient age, sex, race, ethnicity, language spoken, and comorbidities, as well as the patient's neighborhood-level SES.

4.5. Data collection.

The primary outcome will be measured via analysis of EHR records and chart review, as defined above.

For the secondary outcomes that involve medication prescription orders and fills, and for the exploratory outcomes, we will use data available from KPNC computerized sources, including HealthConnect (HC, aka EPIC) EHR data (from Clarity) and EPIC access logs. For each patient with a refill request, EHR data will be used to identify all ADHD medication prescriptions ordered and filled (sold) during the study period.

Patient care experience will be evaluated by surveying a sample of parents selected at random in both the Pharmacist Care and PCP Care groups. We have designed a short survey that takes no more than 5 to 10 minutes to complete. The survey will be fielded by email, mail, and telephone. Due to the fact that we are asking about a specific care experience and patients' recall fades quickly after 2 weeks, we will field the survey using all 3 modes in a relatively efficient sequence. A letter containing a description of the study, language regarding informed consent and confidentiality, and the survey will be sent by mail on day 7 after the secure message has been replied to, and an email with a link to the online version will be sent on day 11. Telephone administration will be attempted (up to 4 attempts total) starting on day 14 for those who have not replied to the paper or online survey. Only the first RAR will be eligible to generate a survey request. A gift card valued at \$10 to thank patients for considering participation will be included in the mailing. Responses will be treated as confidential and data will be aggregated, with no individual identifiers associated with data presented in reports.

Parent-reported outcomes will be reported on a 5-point scale and will include:

- a. Perceived effectiveness of the initial reply in addressing the request
- b. Perceived quality of care for the request overall

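### Days to fill run from the request, and no pre-specified covariate covers medicine the child still has, so this secondary comparison may lose precision

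*Combined protocol and SAP*

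**What the plan says.** Section 4.4.1 defines secondary outcome (c) as "Days from the secure message request to the prescription being filled (sold), among patients who had a prescription ordered". It also lists a companion timing outcome (b): "Hours from the secure message request to the prescription order being placed, among patients who had a prescription ordered".

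Section 4.6 analyzes the timing outcomes with "linear mixed regression models, providing point and interval estimates of between-group differences in mean outcomes", and adds: "If the numbers of days have a skewed distribution, log transformation will be used". On covariates it says "The approach to inclusion of covariates and sensitivity/exploratory analyses is as described for Aim 1". The Aim 1 set is study group plus "patient socioeconomic status (using the Neighborhood Deprivation Index), patient age, sex, race and ethnicity, and comorbidity score". The general covariate list in 4.4.2 adds language. Neither list includes last fill date, days' supply or supply remaining.

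Section 4.6 also allows sensitivity analyses with further covariates, chiefly those imbalanced by chance. None is named. Section 4.5 limits the dispensing data: "EHR data will be used to identify all ADHD medication prescriptions ordered and filled (sold) during the study period".

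The Aim 2 power statement in 4.8 concerns time to order. The documents give no power figure for days to fill.

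**The concern.** These are refills, so the children already take the medicine, and section 2 treats it as a controlled substance. A parent may ask while some supply is left. If the sale then waits until about run-out, its date depends partly on how early the parent asked, which study group does not influence.

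Remaining supply is fixed before anyone handles the request and could be strongly prognostic for days to fill. The planned demographic and comorbidity covariates are unlikely to stand in for it. Left out, its variation goes into the residual and widens the interval for the group difference. At stake is the precision of one secondary outcome. It is one that the abstract names and for which the protocol hypothesizes faster fills.

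**Working it through.** **1. The plan's own figure.** Inputs from 4.8: N = 315, 63 clusters of 5, ICC 0.03, 80% power, two-sided alpha 0.05.
- Design effect = 1 + (5 − 1) × 0.03 = 1.12.
- Detectable effect = (1.960 + 0.842) × √(4 × 1.12 / 315) = 0.334 SD, as stated.
- Implied standard error of the standardized difference = 0.334 / 2.8016 = 0.119.
- Power at standardized effect ES = Φ(ES / 0.119 − 1.96).

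The plan states 0.334 for time to order. It is borrowed here only to fix N and ICC.

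**2. Illustrative model (assumptions, not in the documents).** Days to fill = max(order delay, supply left) + pick-up lag. Order delay is exponential with mean 1 day (pharmacist) or 2 days (PCP). Pick-up lag is exponential with mean 1.5 days. A share of requests have supply left, uniform from 0 to L days, and the rest have none. Standard deviations come from simulation.

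**3. Difference in days.** With no supply left it is 2 − 1 = 1.00 day. With supply uniform on 0 to L, the mean of max(order delay, supply) for mean delay m is L/2 + (m²/L)(1 − e^(−L/m)), so the group difference is:
- L = 7: [4(1 − e^(−3.5)) − (1 − e^(−7))] / 7 = 0.41 day.
- L = 14: [4(1 − e^(−7)) − (1 − e^(−14))] / 14 = 0.21 day.

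With half of requests early, the overall difference is 0.5 × 1.00 + 0.5 × 0.41 = 0.70 day, or 0.5 × 1.00 + 0.5 × 0.21 = 0.61 day. In simulation it is the same unadjusted, adjusted for supply, or with the clock restarted at the later of request and run-out.

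**4. Precision.**

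| Early requests, supply left | ES unadjusted | ES adjusted | Power unadjusted | Power adjusted |
|---|---|---|---|---|
| None early | 0.46 | – | 97% | – |
| 10%, up to 7 days | – | – | 92% | 96% |
| 25%, up to 3 days | – | – | 95% | 95% |
| 50%, up to 7 days | 0.27 | 0.35 | 62% | 83% |
| 50%, up to 14 days | 0.14 | 0.31 | 21% | 74% |

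Example, third-to-last column to last: Φ(0.35 / 0.119 − 1.96) is about 83%.

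The plan's log transformation recovers part of the loss in the worst row: about 40% unadjusted against 74% adjusted. In the 50%, 7-day row it changes little (63% against 81%).

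**5. Other mechanisms.** With mean pick-up lag 1 day and days to fill = max(order delay + lag, supply), 50% early and up to 7 days left gives a 0.77-day difference, with power 88% unadjusted and 98% adjusted. If supply simply adds to the delay, the difference stays at 1.00 day and unadjusted power falls from 99% to 82%. Precision falls under every mechanism tried. The difference in days shrinks only where the fill waits for run-out.

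**The case against.** **The mechanism is assumed.** No section says that children have medicine left, that sales wait for run-out, or how many parents ask early. This stands. The size cannot be derived from the documents, and inputs just as plausible make the gain negligible.

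**Nothing is biased.** A reader might infer that days to fill hide a real speed difference and that adjustment would bring it back. The documents do not support that. If a child has supply and the fill waits for it, a faster order does not bring the fill forward. The smaller difference is then the true effect on request-to-fill time, and adjustment leaves it unchanged.

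**A null would not conceal faster handling.** A reader might also infer that a one-day service gain could go unseen. Outcome (b), hours to order, measures it directly, and time to order is what Aim 2 was powered on. This limits the point to the separate question about fills.

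**Section 4.6 partly covers it.** The sensitivity analyses admit further covariates, and the plan undertakes to note any that improve precision. The cover is partial: supply is not named, the focus is chance imbalance, and a strongly prognostic but balanced variable need not be picked up. A covariate chosen after seeing the data is also less convincing than one named beforehand.

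**Conclusion.** The omission is confirmed: the clock for days to fill starts at the request, and no pre-specified covariate reflects supply remaining. The consequence is conditional. If a substantial share of parents ask early and sales wait for run-out, precision may fall materially, from 83% power to 62% or from 74% to 21% (74% to 40% on the log scale) in the two main illustrations. At 10% early with up to 7 days left, or 25% with up to 3 days, almost nothing is lost.

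Randomization balances supply between groups in expectation, so this is neither confounding nor a threat to validity. The point concerns one secondary outcome and is low priority. It is worth making because the remedy is specific and cheap.

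**What to change.** 1. In 4.6, pre-specify days of supply remaining at the request as a fixed covariate in the days-to-fill model only. Define it as last fill date + days' supply − request date, floored at 0.
2. In 4.5, extend the extraction to fills before May 6 and include days' supply. Without this look-back the covariate cannot be built for many requests.
3. As a supporting analysis, report the group difference separately for requests with no supply left and with some left. This shows the difference where supply cannot hold back the fill, which covariate adjustment does not.
4. State that days to fill will be interpreted alongside hours to order.

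The cost is some SAP wording, a short look-back, a days'-supply field that 4.5 does not currently list, and one more covariate in a model planned for about 300 records. No patient contact is needed. Run-out dates will carry some error where doses are not taken as dispensed, which reduces the precision gained.

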Pharmacist Management of Attention Deficit Hyperactivity Disorder
Medication Refill Requests

Study Protocol and Statistical Analysis Plan

[name], MPH, [name], [name], PharmD, E. [name], [name], MA, [name], BA, [name], MS, [name], [name], [name]

From The Permanente Medical Group (Division of Research, Virtual Care Team, Adult and Family Medicine regional leads, and TPMG Consulting Services) and Pharmacy Services, Kaiser Permanente Northern California, all in Oakland, CA

Version date: August 27, 2024

NCT06388694

Abstract

Importance. Enhancing the management of messages from patients and providing high-quality, consistent care are top priorities for The Permanente Medical Group (TPMG) and Kaiser Foundation Hospitals/Health Plan (KFH/P). A special extension of the Ryan Haight Act currently enables providers to prescribe controlled substances via telehealth interactions but expires in December 2024. Information about the quality of care provided via telehealth prescribing of controlled substances by pharmacists and primary care physicians would be helpful to inform care delivery within Kaiser Permanente and beyond.

Objective. To compare pharmacist management of refill authorization requests for attention deficit hyperactivity disorder (ADHD) medications with physician management regarding quality of care, efficiency of service, and parent satisfaction.

Design, setting, and participants. This cluster randomized clinical trial will include parents of children in Kaiser Permanente Northern California who request ADHD medication refills via secure messages from April 29 to June 28, 2024. Of KPNC's 63 facilities eligible for inclusion, we will assign 32 to Pharmacist Care and 31 to PCP Care.

Intervention. In the intervention group, a regional team of pharmacists will manage electronic refill authorization requests for ADHD medications using a standard protocol. In the comparison group, pediatricians will manage these visits using a similar protocol.

Main Outcomes and Measures. The primary outcome is whether a patient who did not have a weight recorded in the 6 months before the refill request was referred for a primary care follow-up visit. Secondary outcomes are the days from the secure message request to the prescription order and medication fill, and parent satisfaction.

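### The primary analysis is called intention-to-treat, yet requests from PCP Care facilities that add local pharmacists are censored, and no analysis keeps them as randomised

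*Combined protocol and SAP*

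**What the plan says.** Three statements in section 4.6 bear on this point.

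- Primary population: "The primary analysis will treat each patient as part of the group to which their facility was assigned (intention-to-treat".
- Departures in the Pharmacist Care arm: the plan foresees that "some patients in the Pharmacist Care group might have unintentional crossover and be handled by physicians instead of pharmacists". No exclusion follows. These requests stay in their assigned arm, and for care actually received "we will conduct a secondary analysis in which patients are grouped based on the initial management approach they actually received".
- Departures in the PCP Care arm: a facility may drop out "if they were assigned to PCP Care but add local pharmacist management, thus diverging from their assigned group". The consequence is that "ADHD medication refill requests to such a facility will be censored as of the dropout date (the date that local pharmacist management began".

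The dropout rule is not tied to a secondary analysis. It speaks of refill requests in general, so it also reaches the secondary outcomes. The other analyses named in section 4.6 are models with added covariates and analyses of effect modification.

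**The concern.** Censoring here means discarding data because a cluster departed from its assignment after randomisation. An intention-to-treat analysis is meant to rule that out. Departures in Pharmacist Care are kept and examined separately, while the facility-level departure in PCP Care is removed.

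None of the planned analyses restores the removed requests to their randomised arm. The secondary analysis by care received does not say whether it includes them, and if it did, it would group them by clinician. Yet the data are not lost: section 4.4.1 takes the primary outcome from EHR data and chart review, and both remain available after a facility switches.

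At stake is whether the headline contrast is what its label says. The Abstract would treat pharmacist outcomes that are as good as or better than PCP outcomes as grounds for continuing the service, so a reader needs to know which contrast is being shown.

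**Working it through.** **Inputs from the documents.** The Abstract says "we will assign 32 to Pharmacist Care and 31 to PCP Care". Section 4.8 gives 95 patients for the primary outcome, ICC 0.03, 80% power, two-sided alpha 0.05, and a detectable contrast of 50% (PCP) versus 77% (pharmacist).

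**Reproducing the plan's figure.** With 47.5 patients per arm and design effect 1 + 0.5 × 0.03 = 1.015, solve p − 0.50 = (1.96 + 0.84) × √(1.015 × [0.25 + p(1 − p)]/47.5). This gives p = 76.8% (77.5% with pooled variance), so the stated 77% reproduces.

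**Assumptions.** The documents give no number of switches, no timing and no referral rate after a switch. Let k be the number of PCP facilities that switch, f the share of the period before the switch, and q the referral rate afterwards. Facilities are taken as equal in size, and switching facilities as otherwise like the rest.

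**Gap.** The censored difference is 77 − 50 = 27.0 points. Keeping all requests raises the PCP rate by k(1 − f)(q − 0.50)/31, which is therefore the amount by which the censored difference exceeds the intention-to-treat difference.

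| k | f | q | Gap (points) | Intention-to-treat difference |
|---|---|---|---|---|
| 1 | 0.5 | 0.77 | 0.44 | 26.6 |
| 3 | 0.5 | 0.77 | 1.31 | 25.7 |
| 5 | 0.5 | 0.77 | 2.18 | 24.8 |
| 5 | 0 (day 1) | 0.77 | 4.35 | 22.6 |
| 5 | 0.5 | 0.60 | 0.81 | 26.2 |
| 5 | 0.5 | 0.50 | 0 | 27.0 |
| 5 | 0.5 | 0.35 | −1.21 | 28.2 |

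Under section 4.8's other scenario (80% versus 98%), five mid-period switches running at 98% give 5 × 0.5 × 0.18/31 = 1.45 points.

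**Against sampling error.** Splitting 95 patients 31:32 gives 46.7 and 48.3. The mean cluster size is 95/63 = 1.51 and the design effect is 1 + 0.51 × 0.03 = 1.015. SE = √(1.015 × [0.25/46.7 + 0.1771/48.3]) = 0.0957, so the half-width is 1.96 × 0.0957 = 18.8 points.

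Section 4.8 assumes 9 weeks, but section 4.1 sets a 7-week study period. Scaling gives 95 × 7/9 = 73.9 patients (36.4 and 37.5), mean cluster size 1.17 and design effect 1.005. SE is then 0.108 and the half-width 21.2 points. The gaps in the table do not depend on sample size.

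**Selection.** Switching facilities may differ from the rest. Suppose both arms truly average 50%, and five facilities that would have run at 30% leave on day 1. The remaining PCP rate is (0.50 − 0.1613 × 0.30)/(1 − 0.1613) = 0.5385, a shift of −3.8 points in pharmacist minus PCP. If they would have run at 70%, the shift is +3.8. With one facility it is 0.7 either way.

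**Requests removed**, at 95 patients: 46.7 × k(1 − f)/31. This is 0.75, 2.26 and 3.77 for 1, 3 and 5 mid-period switches, and 7.5 for five on day 1.

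**Power** (pooled two-proportion test, same design effect; 0.784 with no switch), censored versus all kept, for mid-period switches at q = 0.77:
- k = 1: 0.781 versus 0.771
- k = 3: 0.774 versus 0.744
- k = 5: 0.767 versus 0.716

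For k = 5 at q = 0.50 the order reverses: 0.767 versus 0.784.

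**The case against.** The best defence is that the two departures differ in kind. Leakage in Pharmacist Care happens request by request, because PCPs still see those requests in their inboxes (section 4.2). The PCP Care event is a whole facility moving to a third model. The intervention is that "a regional team of pharmacists will manage electronic refill authorization requests for ADHD medications"; local pharmacists are not that team, so a switched facility delivers neither arm's care. Stopping its data at an objective date answers a recognisable question: regional pharmacists against PCP care while PCP care is being delivered. Keeping the requests can dilute the contrast and cost power in a trial that, by its own account, can detect only large differences.

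Much of this stands. It justifies reporting the censored analysis, and it explains the asymmetry. It does not make the censored set intention-to-treat. Changing only the label would cure the wording but still leave no as-randomised result.

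Three stronger readings are tempting and are not supported:

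- **That the rule favours pharmacist care.** This needs a post-switch rate above the PCP rate. The documents give none, and selection of facilities can push either way.
- **That the result is in fact affected.** The plan says only that a facility may drop out, and nothing shows that one did. Requests before the switch are kept in any case.
- **That the rule was written with results in view.** The title page reads "Version date: August 27, 2024", after the study period in section 4.1 closed on June 21. That does not show when the rule was written or whether anyone had compared the arms. It means only that any switches can now be stated.

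**Conclusion.** The concern holds as an inconsistency within section 4.6: the primary analysis is labelled intention-to-treat, the dropout rule makes it something else for one arm if it is ever triggered, and no as-randomised analysis is available as a check. It should be corrected, but the likely numerical effect is modest.

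For 1 to 5 mid-period switches at an assumed post-switch rate of 77%, the gap is about 2% to 12% of the 18.8-point half-width (0.44/18.8 to 2.18/18.8). For five on day 1 it is 23% (4.35/18.8). Five facilities is an illustrative limit, not a bound taken from the documents. The gap is nil if no facility switched or if the referral rate did not change, and it reverses if the rate fell.

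**What to change.** In section 4.6, define the primary analysis as all refill authorization requests from all 63 randomised facilities over the full study period, under the assigned arm. Move the dropout-censored analysis to a named sensitivity analysis, and apply the same pair of analyses to the secondary outcomes. Report how many facilities switched and on what dates, including zero.

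The cost is a change of wording plus chart review of the retained requests: about 1 to 8 at 95 patients, a count that rests on pilot secure-message volume and nine weeks. If switched facilities reach 77%, there is also some loss of power, for example 0.77 to 0.72 for five mid-period switches. Dilution would also pull the arms together, and the Abstract counts similarity in the programme's favour. Both analyses should therefore be shown side by side.
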